## Appendix B: Trigriluzole (BHV-4157) + Anti-PD-1 Lab Appendix

### I. Overview of samples to be collected

Tumor biopsies will be performed and blood samples will be collected for correlative analyses. We will measure changes in the tumor microenvironment and peripheral blood in pre- and post-treatment samples in the following categories:

- Immune cell phenotypes and gene expression
- Angiogenesis markers
- Metabolic effector molecules
- Exosome biogenesis
- Pharmacokinetic (PK)

The expected sample size is 12 to 27 subjects. Detailed Study Calendars are located in the Protocol. The following table lists the samples that are expected to be collected from each subject.

Time	Samples needed
Screening or Baseline	
 
• Archival tissue (block or 6-10 unstained slides) when available
 
• Tumor biopsy (optional but strongly encouraged)
 
• Peripheral blood collection for biologic correlative studies (1 green top tube and 1 red top tube)
 

Week -2	
 
• PK samples x 3 (lavender top tubes)           
 
1. Pre-treatment
 
2. 2 hours post-trigriluzole (window +/- 30 minutes)
 
3. 4 hours post trigriluzole (window +/- 30 minutes)
 
 
 

Week 1	
 
• Tumor biopsy (optional but strongly encouraged)
 
• Peripheral blood collection for biologic correlative studies (1 green top and 1 red top tube)
 
• PK sample (lavender top)
 

Week 7	
 
• Tumor biopsy (optional but strongly encouraged)
 
• Peripheral blood collection for biologic correlative studies
 
• PK sample (lavender top)
 

Week 13	
 
• Peripheral blood collection for biologic correlative studies (1 green top and 1 red top tube)
 

## **II. Handling of archival tumor tissue**

Archival tumor tissue (for example, in paraffin blocks or pathology slides) should be logged and labeled in BRS and then delivered to the laboratory and kept at room temperature until analysis.

## **III. Collection of fresh tumor tissue**

- a. Method of biopsy: Excisional biopsy or punch biopsy is preferred over core needle biopsy for purposes of tissue sampling for correlative studies. An optimal size is 15 x 15 mm, but 5 mm x 5 mm is also acceptable. There is no minimum size that is required. If a core needle biopsy is performed, 1-3 cm of core is recommended. If the lesion is < 2 cm in longest diameter and it is a RECIST target lesion, care should be taken to ensure that the overall size of the target lesion is not affected by the tissue sampling. In this case, a small excisional biopsy or core biopsy should be performed.
- b. The RCINJ Biospecimen Repository Service (BRS) will process, label and store the tissues samples.
- c. Fresh tumor tissue for Western blotting will be collected by biopsy and immersed (completely) in sterile cold (2-7°C) RPMI in a sterile specimen cup (for example, VWR catalog# 15704-088) on ice.
- d. Fresh tumor tissue for murine experiments will be collected in sterile cold (2-7°C) RPMI in a sterile 50 ml centrifuge tube.
- e. The specimen cup or centrifuge tube will be labeled with the patient ID, date, and time of tumor tissue collection.
- f. The sample will be immediately transported on ice from the collection site to the BRS laboratory.
- g. Tissue processing should be performed as soon as possible after tissue collection/receipt (maximum time from tissue acquisition and processing should be no more than 3 hours).

## **IV. Processing of tumor tissue**

The RCINJ Biospecimen Repository Service (BRS) will process, label and store the tissues samples until delivery to the analysis lab.

As clinical samples are often small, the allocation of small tumor samples for different correlative studies will be determined per the following table:

### **Prioritization Table for Fresh Tumor Biopsies**

Protocol Number: RCINJ# 051707

PI Name: [name]

Protocol Title: A Phase I Study to Evaluate the Safety of Trigriluzole (FC-4157/BHV-4157) in Combination with PD-1 Blocking Antibodies

81

RESERVED FOR IRB STAMP  
DO NOT MODIFY THIS SPACE

Form Version v120116

**RUTGERS | eIRB**  
**APPROVED**

IRB ID: Pro20170000453  
Approval Date: 10/4/2019  
Expiration Date: 4/3/2020

Priority Level	Type of Preserved Tissue	Biomarker Analysis Method
1st	Flash frozen in liquid nitrogen	
 
- Western blotting           
 
○ Expression of MAPK and PI3K/AKT signaling pathway components
 
○ M-CSF and CCL2 expression
 
○ HIF-1a, IL-8, and VEGF expression
 
 
 
Gene expression profiling
 

2nd	Formalin fixed paraffin embedded (FFPE)	
 
- IHC           
 
○ GRM1 expression
 
○ pERK and pAKT
 
 
 
- H&E
 
- Lymphocytic Infiltration
 

		○

Fat will be trimmed from the tumor. Tumor tissue specimens will be measured in the 2 longest dimensions. Tumor tissue will be sectioned into specimens by the following prioritization rules:

**Prioritization Rules for Allocation of Tumor Tissue at Baseline**

Tumor Size in 2 dimensions	Allocation of Tissue
<5 x <5 mm	
Cut into 2 equal sections.
 
 
2. Allocate one of the sections to liquid nitrogen
 
3. Allocate one of the sections to formalin
 

≥5 x ≥5 mm	
Split tumor into 3 equal sections:
 
 
1. Allocate one third to RPMI
 
2. Allocate one third to liquid nitrogen
 
3. Allocate one third to formalin
 

**Prioritization Rules for Allocation of Tumor Tissue at Weeks 1 and 6**

Tumor Size in 2 dimensions	Allocation of Tissue
<5 x <5 mm	1. Allocate entire specimen to liquid nitrogen
≥5 x ≥5 mm	Split tumor into 2 equal sections. 1. Allocate one of the sections to liquid nitrogen 2. Allocate one of the sections to formalin

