### **Analysis Plan for Secondary Endpoints**

Clinical Secondary Endpoints. The frequency of AEs and SAEs will be recorded. Clinical measures of efficacy will be described, including overall survival, progression-free survival, etc. (see Secondary Endpoints above). Descriptive statistical will be used, except where otherwise specified. Continuous variables will be presented by summary statistics (such as mean, median, standard error and 90% CI) and the categorical variables by frequency distributions (i.e., frequency counts, percentages and 90% CI).

Correlatives. We will collect pre- and post-treatment tumor samples from responders and non-responders to test for differences in signal transduction in key pathways (MAPK, Pi3K/AKT), presence of TILs and other immune effector cells, PD-L1 expression, the expression of VEGF, IL-8, CD34, CCL2, M-CSF, and immune-related gene expression profile. We will determine if the presence of GRM1 expression, activating mutations in B-RAF or N-RAS, or PTEN inactivation (or activating B-RAF mutations and PTEN inactivation together) in the pre-treatment tumor samples correlates with response to therapy. We will examine the change in key pathways before and after the trigriluzole monotherapy lead-in period (Baseline vs. Week 1) and compare to the samples taken after exposure to combination therapy (Week 7).

We will also collect pre- and post-treatment peripheral blood samples from responders and non-responders and determine the expression of VEGF, IL-8, CD34, CCL2, and M-CSF, and changes in the quantity and contents of tumor-derived exosomes. We will determine if the expression of these markers in pre-treatment peripheral blood samples correlates with response to therapy. Next, we will compare the pre-treatment and post-treatment blood and tumor samples to see if response to treatment correlates with activation or suppression of signal transduction through the MAPK and PI3K/AKT pathways, changes in immune effector cells in the tumors and peripheral blood, or changes in the quantity or contents of peripheral blood exosomes.

Treatment effect for each patient will be measured as paired differences between pre- and post- measurements of these parameters at various times. Transformation of the data will be performed if appropriate, e.g. log transformation, and hence treatment effect will be expressed on a log scale.

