## VII. Correlative Analyses

### A. Immunophenotyping

- a) Immune cells in the blood and the tumor will be profiled using cells obtained from RPMI-preserved tumor tissue samples and PBMCs (controls) obtained from peripheral blood using flow cytometry to look for TILs, Tregs, MDSC, TAM and other immune cells.
- b) Tumor biopsy tissue will be preserved in RPMI solution and PBMCs frozen at -80°C or colder and delivered to the Rutgers CINJ Immune Monitoring Core.
- c) Tumor samples will be dissociated into a single-cell suspension by the Rutgers CINJ Immune Monitoring Core, as described below.
- d) Cell in single suspension of tumor or PBMCs (controls) will be analyzed by the Rutgers CINJ Immune Monitoring Core utilizing 14-parameter flow cytometry with an LSR-II flow cytometer, whereby cells will be stained with fluorescent antibodies to the validated cell markers (purchased primarily from eBioscience, Biolegend, and BD Biosciences).
- e) Cell population ratios will include identifying cells as cytotoxic CD8+ T cells (Tcs), CD4+ helper T cells (Ths) regulatory CD4+ T cells (Tregs), MDSCs, B cells, NK cells, and DCs.
- f) Markers evaluated will include CD3, CD4, CD8, CD11b, CD11c, CD14, CD16, CD19, CD25, CD33, CD45RA, CD56, CD80, CD86, CCR7, FoxP3, Granzyme B, HLA-DR, NKp46, PD-1, and PD-L1.
- g) Specifically:
  - (i) The tumor tissue will be mechanically dissociated upon receipt using a GentleMACs OctoDissociator (Miltenyi) using the B\_01 program.

- (ii) The resulting tumor-derived cells will be passed through a 70 µm screen (BD Biosciences) to ensure a single cell suspension, and washed in PBS, and frozen down, as described previously at 2x10^6 in cryopreservation solution at -80°C or colder.
- h) Frozen cells from tumor tissue will be thawed quickly by immersion of the bottom 90% of the cryovial in a 37°C water bath and washed once in PBS (with centrifugation and reconstitution of the cell pellet in 50 µl PBS per sample in a 96 well plate) prior to flow cytometric antibody staining.
- i) For extracellular markers:
- j) Plates with cells to be stained will be centrifuged at standard conditions (4°C, 1500 rpm, 5 min) and decanted by inversion.
- k) Extracellular marker antibodies will be added at titrated concentrations (for example, 0.5 µl antibody in 50 µl of PBS for antibodies used at 1:100).
- l) The plate will be incubated in the dark for 30 minutes at room temperature and then centrifuged at standard conditions and washed once with PBS.

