- a) Analysis of cytokines within the tumor microenvironment will be performed using tumor tissue obtained from RPMI-preserved samples and frozen serum samples.
  - b) Tumor biopsy tissue will be preserved in RPMI solution at each site and serum frozen obtained from peripheral blood and delivered to the Rutgers CINJ Immune Monitoring Core.
  - c) Tumor tissue samples will be mechanically homogenized upon receipt using the GentleMACs OctoDissociator (Miltenyi), as per the manufacturer instructions.
  - d) Samples will be frozen at -80°C or colder until analysis of cytokines.
  - e) Cytokine standards will be prepared as per manufacturer instructions from the manufacturer's master standard stock, for the cytokines of interest.
  - f) Biolegend flow cytometry-based LEGENDplex technology for cytokine multiplexing will be utilized. The LEGENDplex Human Anti-Virus Response Panel (Cat. No. 740390) is a bead-based multiplex assay, utilizing fluorescence-encoded beads suitable for use on flow cytometers. This panel allows simultaneous quantification of 13 human proteins, including interferons ( $\alpha$ ,  $\beta$ ,  $\gamma$ , and  $\lambda$ ), interleukins (1, 6, 8, 10, 12), TNF- $\alpha$ , IP-10 and GM-CSF.
  - g) The panel has been validated by the manufacturer and is a standard assay of the Immune Monitoring Core at Rutgers CINJ for determination of cytokine levels using flow cytometry (LSR2; BD).
  - h) Details regarding accuracy, precision, and published references for this system are available from the manufacturer.
  - i) The plate will be analyzed on an LSR-II Flow Cytometer, as per the manufacturer instructions within 1 hour of last incubation.

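### On-treatment biopsies get no RPMI tissue, so the planned pre/post change in tumor flow-cytometry phenotypes, tumor cytokines and RPMI-derived protein cannot be computed for any subject

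*Combined protocol and SAP*

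**What the plan says.** **Allocation of tissue (Appendix B, section IV).** At baseline, a specimen of at least 5 x 5 mm is cut in three. The first instruction is "Allocate one third to RPMI"; the other thirds go to liquid nitrogen and formalin. A smaller baseline specimen is halved between liquid nitrogen and formalin.

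The on-treatment table is headed "Prioritization Rules for Allocation of Tumor Tissue at Weeks 1 and 6". For small specimens it says "Allocate entire specimen to liquid nitrogen". For larger ones it says "Split tumor into 2 equal sections. 1. Allocate one of the sections to liquid nitrogen 2. Allocate one of the sections to formalin". RPMI appears in neither row.

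**Tissue required by the assays (Appendix B, section VII).** Under Immunophenotyping: "Immune cells in the blood and the tumor will be profiled using cells obtained from RPMI-preserved tumor tissue samples". Under Cytokine levels: "Analysis of cytokines within the tumor microenvironment will be performed using tumor tissue obtained from RPMI-preserved samples". Section VII.B takes the protein for expression profiling from RPMI-preserved tumor cells as well.

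**Planned analysis.** Section 6.1, Analysis Plan for Secondary Endpoints, measures each patient's treatment effect on the correlative parameters as a paired pre/post difference. It also asks whether response goes with changes in immune effector cells, in tumor as well as blood. Appendix B, section I, likewise promises change between pre- and post-treatment samples for immune cell phenotypes.

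**Biopsy times.** Section 1.8 (Tumor Sampling), footnote 6 of both treatment calendars in section 1.10, and the sample table in Appendix B, section I, all place the on-treatment biopsies at Weeks 1 and 7.

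**The concern.** A paired difference needs the same assay at both times. Three tumor assays are tied to a preservation medium that the on-treatment rules never supply, so the plan promises a change score with no second value.

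The affected measures sit close to the trial's rationale. Section 1.2 argues that blocking GRM1 lowers suppressive macrophages, MDSCs and regulatory T cells and raises infiltrating lymphocytes. The flow panel is the only described tumor assay that separates and counts those populations. The formalin-based measures named in the appendix (GRM1, pERK, pAKT, H&E, lymphocytic infiltration, PD-L1) include no Treg, MDSC or macrophage marker. Without RPMI tissue, the suppressive-cell part of the hypothesis has no planned on-treatment cell count in tumor.

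The loss cannot be made good afterwards. The flow method dissociates RPMI tissue on receipt, and the appendix gives no route from flash-frozen or fixed tissue into that assay. Subjects would have accepted the biopsy risk listed in section 4.1.8 without yielding this result.

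**Working it through.** The documents give no sample size, power or error rate for the tumor correlatives, so the check is a count over the written allocation rules.

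**Inputs (Appendix B, section IV)**
- Baseline, under 5 x 5 mm: liquid nitrogen, formalin.
- Baseline, at least 5 x 5 mm: RPMI, liquid nitrogen, formalin.
- On treatment, under 5 x 5 mm: liquid nitrogen.
- On treatment, at least 5 x 5 mm: liquid nitrogen, formalin.

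**Rule.** An assay can be paired only if its medium is held at both times, that is, if the medium lies in the intersection of the baseline and on-treatment sets.

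| Baseline | On treatment | Held at both times | RPMI pair | Formalin pair | Frozen pair |
|---|---|---|---|---|---|
| <5 mm | <5 mm | frozen | no | no | yes |
| <5 mm | ≥5 mm | frozen, formalin | no | yes | yes |
| ≥5 mm | <5 mm | frozen | no | no | yes |
| ≥5 mm | ≥5 mm | frozen, formalin | no | yes | yes |

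**Results**
- RPMI (flow phenotypes, cytokine panel, RPMI-derived protein): 0 of 4 combinations.
- Formalin (lymphocytic infiltration, PD-L1): 2 of 4, whenever the on-treatment specimen is at least 5 x 5 mm.
- Liquid nitrogen (Western blot, gene expression): 4 of 4.

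**In subjects.** The planned total is 9 + 3 = 12 to 21 + 6 = 27. Because no combination yields an RPMI pair, the number of subjects with one is 0 of 12 to 27, whatever share agrees to the optional biopsies.

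**Does RPMI at collection rescue this?** Appendix B, section III, places fresh tissue in cold RPMI for transport. That step comes before allocation. The on-treatment table then sends the whole specimen, or both halves of it, to liquid nitrogen or formalin.

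**Does the Week 6 label rescue it?** No. Read strictly, Week 7 has no allocation rule under its own name. No rule supplies RPMI tissue at Week 7, and Week 1 is explicitly covered without RPMI.

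**Effect of a three-way split on treatment.** Adding RPMI to the larger on-treatment row gives an RPMI pair in 1 of 4 combinations, when both specimens are at least 5 x 5 mm. The documents do not give the share of subjects who would qualify. Assuming 25%, 50% or 75%:
- N = 12: 3, 6 or 9 pairs.
- N = 27: 6.75, 13.5 or 20.25, so about 7, 13 to 14, or 20 pairs.

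**The case against.** The strongest reply is that much of the tumor analysis survives. A reader might infer that no change in tumor immune cells can be measured at all. The documents do not support that. The priority table in section IV lists lymphocytic infiltration under formalin-fixed tissue, PD-L1 is stained on formalin-fixed tissue, and TILs with PD-L1 is the first correlative endpoint in section 1.1.3. These can be paired when the on-treatment specimen is large enough. Gene expression is listed under frozen tissue and can be paired at either size. Even within cytokines, IL-8 is also planned by Western blot on frozen tissue.

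A reader might also think the comparison with Week 7 fails as a whole, given the words "compare to the samples taken after exposure to combination therapy (Week 7". That sentence in section 6.1 concerns key signaling pathways, which are run by Western blot on first-priority frozen tissue. That comparison is intact.

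Nor is a named secondary objective defeated. Section 1.1.1 seeks markers of response in the microenvironment, which baseline RPMI tissue can serve. Change is a correlative endpoint. Section 6.1 calls these analyses descriptive, possibly too small to test, and aimed at feasibility.

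These points limit the scope and the stakes, and all of them stand. They do not remove the gap: feasibility of paired tumor flow cytometry cannot be shown if its tissue is never allocated.

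Two uncertainties remain. Section 1.8 refers to a Lab Manual, and it is unclear whether Appendix B is that manual. In addition, the small-specimen list at baseline starts at item 2 and the last row of the priority table is blank, so a line may be missing there. The on-treatment table's numbering is intact, so this does not explain its lack of RPMI.

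**Conclusion.** The plan is inconsistent as written. Paired change in tumor flow-cytometry phenotypes, the tumor cytokine panel and RPMI-derived protein is available for 0 of 12 to 27 subjects. This rests on the allocation tables in Appendix B being the operative rules and on the assays being run on the tissue the appendix names. The optional analyses in Appendix B, section IX, could add further staining if samples allow, but they define no on-treatment replacement for these measures.

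The consequence is confined to descriptive correlatives. The formalin-based and frozen-tissue measures listed above remain pairable, and the MTD/RP2D endpoint does not depend on any of this. The Week 6 label is a separate, smaller discrepancy.

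**What to change.** In the on-treatment table of Appendix B, section IV, apply the baseline three-way split (RPMI, liquid nitrogen, formalin) to specimens of at least 5 x 5 mm, and keep the frozen-only rule for smaller ones. No extra biopsy is needed. The cost is that the frozen and formalin shares of larger specimens fall from 1/2 to 1/3, a loss of (1/2 − 1/3) / (1/2) = one third of each. That includes the formalin tissue used for infiltration and PD-L1. RPMI pairs will exist only where both specimens reach 5 x 5 mm.

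If RPMI was left out on purpose, to protect the higher-priority portions of small samples, keep the table. Then state in section 6.1 and in Appendix B, sections I and VII, that these tumor assays are baseline-only, and drop the paired-change claim for them. That costs text only, but gives up the on-treatment count of suppressive cells in tumor.

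Either way, correct the table heading to Weeks 1 and 7. The same edit should say which row applies when only one dimension is under 5 mm, as a narrow core would be; at present neither row covers it.

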**1) RPMI preservation**

- A Sterile forceps will be used to gently place the specimen in a sterile labeled cryovial or specimen container (whichever is large enough to hold the tissue full submerged and surround by cold [2-8°C] RPMI. Additional RPMI will be added (under sterile conditions) with the volume required to fully submerge the tissue in the solution and fill the vial/container completely without air pockets.
- B Care should be taken to avoid crushing artifacts and a separate forceps must be used for each specimen to avoid cross contamination.
- C The cryovial/specimen container lid will be secured.
- D The cryovial/specimen container must be kept at 2-8°C and transported immediately to the Immune Monitoring Core laboratory for processing.

**2) Liquid nitrogen storage**

- A The sample will be placed in a 30 ml cryovial and immediately placed in liquid nitrogen.
- B The Dewar will be transported within 60 minutes to the cryo-storage facility
- C The cryovial will be transferred to a liquid nitrogen freezer or a mechanical -80°C freezer for long-term storage until processed for Western Blotting.

**3) Formalin fixation**

- A Specimens intended for formalin fixation should be processed after the completion of other fresh tissue procedures, such as flash freezing and submersion in RNA stabilizing reagent.
- B The tissue sample should be trimmed such that it is maximally 0.5 cm in thickness. Specimens that exceed this dimension may not allow for adequate perfusion of the formalin.
- C After trimming, the specimen will be transferred to a container with formalin using a forceps. To avoid cross-contamination, a separate forceps should be used for each tissue sample. The volume of formalin should be a minimum of 15-20 times the volume of the

tissue sample - e.g., 20 ml of formalin per 1 cm^3 of tissue. A 15 ml sterile centrifuge or conical tube or alternatively, a specimen cup can be used.

- D The specimen must be completely submerged in the formalin fixative and the container lid securely tightened to avoid any spillage.
- E The tissue will be fixed at room temperature for a minimum of 24 hours and maximum of 48 hours.
- F Formalin should not be discarded down the drain. The chemical disposal plan at the institution will be followed for an appropriate method of disposal.

## **V. Blood sampling for biologic correlative studies**

### **1) Collection of peripheral blood**

- A Research blood collection for correlative studies is to be performed at Baseline/Week - 2, Week 1, Week 7, and Week 13.
  - a) Baseline/Week 2: Approximately 20 mL of blood will be collected in 1 green top tubes and 1 red top tube.
  - b) Week 1: Approximately 20 mL of blood will be collected in 1 green top tube and 1 red top tube.
  - c) Week 7: Approximately 20 mL of blood will be collected in 1 green top tube and 1 red top tube.
  - d) Week 13: Approximately 20 mL of blood will be collected in 1 green top tube and 1 red top tube.
- B The RCINJ Biospecimen Repository Service (BRS) will process, label and store the blood samples.
- C Peripheral blood will be collected by venipuncture into venous blood collection tubes (Red Top tubes with no additive; for example, BD vacutainers catalog# 366430 and Green Top tubes with sodium heparin; for example BD vacutainers catalog# 366480).
- D The samples will be transported at room temperature (18°C to 25°C) in a double container from the collection site to the sample processing laboratory.
- E Red Top tubes for serum processing should be kept sitting upright at room temperature for at least 30 minutes and at most 60 minutes prior to processing to allow clotting. If the blood is not immediately processed after the clotting period, then tubes should be stored (after the 30-60 minutes of clotting time) at 4°C for no longer than 4 h.
- F Green Top tubes for peripheral blood mononuclear cell (PBMC) processing should be kept on a rocker at room temperature until processed (to avoid clotting) and processed as soon as possible (within 4 h maximum) after blood collection.
- G The collection tubes will be labeled with the patient ID, date, and time of venous blood draw.

